7.3 Blinding

Blinding of treatment assignment is critical to the integrity of this clinical study. However, in the event of a medical emergency or pregnancy in an individual participant in which knowledge of the IP is critical to the participant's management, the blind for that participant may be broken by the investigator. The participant's safety takes priority over any other considerations in determining if a treatment assignment should be unblinded.

Before breaking the blind of an individual participant's treatment, the investigator should determine that the unblinded information is necessary, ie, that it will alter the participant's immediate management. In many cases, particularly when the emergency is clearly not related to the IP, the problem may be properly managed by assuming that the participant is receiving active product. It is highly desirable that the decision to unblind treatment assignment be discussed with the BMS Study Director / Medical Monitor (or designee), but the investigator always has ultimate authority for the decision to unblind. The actual TASK of unblinding can be delegated by the investigator to a designee assigned the task on the Delegation of Authority. The Principal Investigator or appointed designee should only call in for emergency unblinding AFTER the decision to unblind the participant has been documented.

For this study, the method of unblinding for emergency purposes is via the Interactive Response Technology (IRT) system. For information on how to unblind in an emergency, consult the IRT manual.

In cases of accidental unblinding, contact the BMS Study Director / Medical Monitor (or designee) and ensure every attempt is made to preserve the blind.

Any request to unblind a participant for non-emergency purposes should be discussed with the BMS Study Director / Medical Monitor (or designee).

Except as noted below, members of BMS Research and Development personnel involved in the study conduct and evaluation, as well as all vendors responsible for the conduct of the trial (protocol team) will remain blinded.

A bioanalytical scientist in the Bioanalytical Sciences department of BMS Research & Development (or a designee in the external central bioanalytical laboratory) will be unblinded to (may obtain) the randomized treatment assignments in order to minimize unnecessary bioanalytical analysis of samples as PK will not be analyzed placebo samples.

An internal Safety Review Committee, independent from the study team, will assess BP data after completion of approximately 8 participants randomized with SBP \geq 115 mmHg and $<$ 130 mmHg in the Sentinel Group. The internal Safety Review Committee will also assess safety results, including hypotension, from the planned interim analysis (IA; [Section 10.3.5](#)).

For the assessment of BP data in the Sentinel Group and for the planned IA, an unblinded statistician and programmer(s), separate from the study team, will be performing the required safety analyses for the internal Safety Review Committee. The internal Safety Review Committee may require access to unblinded treatment codes for individual participants. Additional designated

staff of BMS Company will be provided with aggregate data from the IA for future study planning as described in the statistical analysis plan.

7.4 Dosage Modification

Any decision to decrease the dose level of study drug or discontinue study drug should be based on the investigator's assessment of the participants' clinical stability and in the overall context of the participant's condition. A dose reduction to 1 mg is allowed if certain criteria are met, as described in the section below. Study drug may be also permanently discontinued early as described in the following section.

7.4.1 Dose Down-titration

- On Days 1 through 6, if the participant experiences SBP < 85 mmHg without symptoms related to hypotension, the measurement must be repeated in 30 minutes. If the SBP remains < 85 mmHg the next day's study drug administration should be skipped and dosing should resume at 1 mg, the following day, if SBP is \geq 85 mmHg (ie, after a 1-day drug "holiday", the treatment will resume at a reduced dose).
- On Days 1 through 6, if the participant experiences SBP < 90 mmHg and symptoms of hypotension (such as dizziness, light headedness etc), the measurement must be repeated in 30 minutes. If the SBP remains < 90 mmHg the next day's study drug administration should be skipped and dosing should resume at 1 mg, the following day, if SBP is \geq 85 mmHg and symptoms of hypotension resolved (ie, after a 1-day drug "holiday", the treatment will resume at a reduced dose).
- On Days 1 through 6, if the participant experiences SBP fall \geq 40 mmHg with symptoms of hypotension that in the opinion of investigator preclude further safe dosing of the participant at the initial dose level, the next day's study drug administration should be skipped and dosing should resume at 1mg the following day, if SBP is \geq 85 mmHg and symptoms of hypotension resolved (ie, after a 1-day drug "holiday", the treatment will resume at a reduced dose).
- After dose reduction, the dose cannot be increased again.

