Monitor for Serious Adverse Events (SAEs)	X	All SAEs must be collected from the date of participant’s written consent until 30 days post discontinuation of dosing or participant’s participation in the study if the last scheduled visit occurs at a later time.

Abbreviations: BMI = body mass index; BNP = brain natriuretic peptide; CBC = complete blood count; ECG = electrocardiogram; ER = emergency room; FSH = follicle stimulating hormone; HIV = human immunodeficiency virus; IV = intravenous; NT-proBNP = N-terminal pro-brain natriuretic peptide; NYHA = New York Heart Association; PE = physical examination; RT-PCR = reverse transcription polymerase chain reaction; SARS-CoV-2 = severe acute respiratory syndrome coronavirus 2; SAE = serious adverse event; SOC = standard of care.

^a Screening must occur at least 24 hours post initial emergency room (ER) presentation. Randomization must occur within 8 days post initial ER presentation.

Table 2-2: On-Treatment and Follow-up Procedural Outline (CV019010)

Procedure	Randomization D1 ^a	D 2	D 3	D 4	D 5	D 6	D 7 ^b	D 8 Visit ^c	D 9 ^b	D 10	D 11 ^b	D 12	D 13 ^d	D14 End of Study Visit c,d,e	D30 (± 2 days) Follow -Up Visit ^c	Notes
Safety Assessments																
Targeted PE						X ^f		X ^g						X ^g		Complete before discharge.
Injection site evaluation		X	X	X	X	X	X	X	X	X	X	X	X	X		Injection site evaluation performed daily pre-dose and in the evening. Post-discharge, a home nurse (or site personnel) will evaluate injection site prior to study drug administration.
Physical Measurements	X	X	X	X	X	X ^f		X						X		In hospital weight measurements daily until discharge. Day 1 pre-dose.
Vital Signs	X	X	X	X	X	X	X	X	X	X	X	X	X	X		Pre-dose BP measurement on Day 1 at 0 hour; at 2, 4, 8, 12, 16, 20, 24 hours post dose.

Table 2-2: On-Treatment and Follow-up Procedural Outline (CV019010)

Procedure	Randomization D1 ^a	D 2	D 3	D 4	D 5	D 6	D 7 ^b	D 8 Visit ^c	D 9 ^b	D 10	D 11 ^b	D 12	D 13 ^d	D14 End of Study Visit c,d,e	D30 (± 2 days) Follow -Up Visit ^c	Notes
																
Pre-dose BP measurement on Day 2 at 0 hour, at 2, 4, 8, and 12 hours post dose.
 
Then 4 times a day on following days until discharge, 0, 4, 8, 12 hours. Once participant is discharged home, BP to be measured pre-dose by home nurse. Participant should be in supine position (preferable, based on participant's condition and comfort) and using non-dominant arm for home measurements.

[figure not shown]

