3.3 Benefit/Risk Assessment

The current study is a Phase 2A, multicenter, randomized, double-blind, placebo-controlled, parallel-group study of BMS-986259 in medically stabilized participants currently hospitalized for ADHF. Participants will continue their therapy as deemed necessary for their condition and receive any HF therapy required by HF guidelines. Participants may benefit from an ongoing assessment of their health status in the period of time immediately after discharge from the hospital. It is not known if 2 weeks of therapy with BMS-986259 can provide any symptomatic improvement and 50% of participants will receive placebo. Short-term course of BMS-986259 is not expected to translate into long-term benefit.

In the ongoing Phase 1 study in NHV (CV019-002), BMS-986259's administration was generally safe and well-tolerated. The most frequently reported adverse events (AEs) were cannula site reaction and cannula site pain related to the study procedures to measure RBF and GFR, but unrelated to the study drug. The effect on BP and heart rate (HR) in individual participants appears to be minimal. Formal statistical summaries are not available at this time as the treatment is still blinded, but no clinically significant or symptomatic hypotension has been reported. The doses evaluated thus far have been safe and well-tolerated, with no deaths, serious adverse events (SAEs), or AEs leading to discontinuation reported. In the large serelaxin development program, human recombinant relaxin was generally safe and well tolerated in participants with HF. Bristol-Myers Squibb (BMS) nonclinical and preliminary clinical data and the serelaxin clinical program suggest that the principal risk associated with the use of BMS-986259 is hypotension. Transient reductions in BP are not expected to be associated with long-term sequelae. This study is designed specifically to address this risk, and mitigation strategies are implemented, such as rigorous BP monitoring, both in-hospital and post-discharge, and a dose-modification algorithm in case of symptomatic or asymptomatic hypotension.

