Participants will return for up to three ambulatory visits at the site on Day 8, Day 14, Day 30 (follow-up). If the participant cannot return to the site because of COVID-19 local regulations that prevent visits in-person, these visits can be done at home by the home nurse in discussion with the Principal Investigator (or designee). In addition, at discharge, participants will receive BP measuring device and will be instructed to measure BP if symptoms consistent with hypotension occur. If systolic BP falls below 85 mmHg (on 2 repeated measurements within 30 minutes) and symptoms of hypotension persist, participants will be instructed to report to the study site or another healthcare provider if the study site cannot be reached.

Initially participants with SBP ≥ 115 mmHg will qualify to be randomized 1:1 to receive 3 mg subcutaneous BMS-986259 QD or placebo. After approximately 8 participants with SBP ≥ 115 and < 130 mmHg have completed the treatment period, the Safety Review Committee will review the safety data from this sentinel group and ensure it is safe to proceed with the Main Group, ie., open the recruitment for participants with SBP less than 115 mmHg (but at least 100 mmHg).

The Main Group will include participants with SBP ≥ 100 mmHg, randomized 1:1 to BMS-986259 or placebo. The proportion of participants with SBP > 125 mmHg will be capped at 48 participants.

Study drug may be down-titrated to 1 mg or discontinued according to the criteria described in dose modification in [Section 7.4](#).

In addition, if systolic BP is < 85 mmHg or symptomatic hypotension occurs, the Principal Investigator (or designee; must be a medical doctor [MD]) must be contacted to make a decision

[figure not shown]

as to whether an ambulatory unscheduled study visit or hospitalization is required based on overall clinical assessment. For example, asymptomatic study participants who can walk and have normal urination may not require hospitalization. BMS Study Director/Medical Monitor (or designee) must be notified. A blinded clinical contact will be available 24/7 to answer questions and guide the home nurse as needed.

The study design schematic is presented in [Figure 5.1-1](#).

Figure 5.1-1: Study Design Schematic

Abbreviations: [REDACTED] D = day; ER = emergency room; [REDACTED] QD = once daily; R = randomization; SBP = systolic blood pressure.

^a May be down-titrated to 1 mg or discontinued according to the criteria described in Section 7.4.

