5.5 Justification for Dose

The planned dose for this study (3 mg) has been selected as a pharmacologically active and safe dose, likely to be further studied in Phase 2B, thus safety/tolerability data collected in this study will inform design of the Phase 2B study. The BMS-986259 dose selected for this study (3 mg) was associated with improvement in RBF after single and multiple doses in normal healthy participants (up to 46% increase in RBF). The 3 mg multiple doses in FIH study were also safe and well tolerated by the healthy participants.

In the FIH study (CV019002), single doses as much as 5-fold higher (15 mg) have been safely administered to healthy participants. The observed mean exposures at steady state with repeated 3 mg QD dosing (AUC[TAU]) of 9,070 ng h/mL remain under the mean exposure (AUC[INF]) of 38,200 ng h/mL observed after a single 15 mg dose that was determined to be safe and well tolerated in a healthy participants study (Table 5.5-1).

Based on preliminary results, single dose exposures (C_{max} and area under the concentration-time curve [AUC]) increased in a dose-proportional manner with increasing dose. With multiple doses of 1 mg and 3 mg QD for 14 days, up to 2.5-fold (1 mg) and 2.7-fold (3 mg) accumulation of C_{max} and AUC(TAU) were observed on Day 14 versus Day 1, with steady-state reached within approximately 5 days based on trough concentrations. The geometric mean C_{max} and AUC values observed with a single 15 mg dose and a 3 mg QD dose are listed in Table 5.5-1.

Table 5.5-1: BMS-986259 Exposures in Healthy Participants

Dose	C _{max} (ng/mL) Geometric Mean	AUC (ng·h/mL) Geometric Mean
15 mg single dose	737	38,200*
3 mg QD, Day 1	184	3,420
3 mg QD, Day 14	469	9,070

* AUC(INF)

Abbreviations: AUC = area under the curve; C_{max} = maximum observed concentration; QD = once daily.

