7.1 Treatments Administered

The selection and timing of dose for each participant is as follows:

Table 7.1-1: Selection and Timing of Dose

Study Treatment	Unit dose strength(s)/Dosage level(s)	Dosage formulation Frequency of Administration	Route of Administration
BMS-986259	3 mg ^a , 1 mg ^{a,b}	Daily	Subcutaneous injection
Placebo	N/A	Daily	Subcutaneous injection

^a 5 mg/mL solution will be diluted as described in the pharmacy manual to reach the desired dosage strength

^b 1 mg for down titration only

In the morning on Days 1 through 14 each participant will receive a subcutaneous dose of BMS-986259 or placebo, at approximately the same time.

The time of dose administration of the first dose will be called “0” hour for serum PK reporting.

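### After low blood pressure is confirmed before the morning injection on Days 2 to 6, Section 7.4.1 skips the following day's dose and leaves that morning's dose due

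*Combined protocol and SAP*

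**What the plan says.** Section 7.4.1 of the protocol has three down-titration bullets for Days 1 to 6. The first covers asymptomatic systolic pressure (SBP) below 85 mmHg and the second symptomatic SBP below 90 mmHg, each confirmed by a repeat at 30 minutes. For both, "the next day's study drug administration should be skipped and dosing should resume at 1 mg, the following day", provided SBP is at least 85 mmHg and, in the second bullet, symptoms have resolved. The third covers a symptomatic fall of at least 40 mmHg that the investigator judges to rule out the initial dose. It has no repeat measurement but the same next-day skip. The text describes the result as a one-day drug holiday.

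Dosing is daily (Section 7.1): "In the morning on Days 1 through 14 each participant will receive a subcutaneous dose of BMS-986259 or placebo". Blood pressure times are in Table 2-2:

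- Day 1: "Pre-dose BP measurement on Day 1 at 0 hour; at 2, 4, 8, 12, 16, 20, 24 hours post dose".
- Day 2: "Pre-dose BP measurement on Day 2 at 0 hour, at 2, 4, 8, and 12 hours post dose".
- Later in-hospital days: "Then 4 times a day on following days until discharge, 0, 4, 8, 12 hours".

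Section 3.3 states that "the principal risk associated with the use of BMS-986259 is hypotension" and lists the dose-modification algorithm among the mitigations.

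**The concern.** The skip is tied to the calendar day after the trigger, not to the next injection. That works when the low reading follows the day's injection. When it comes at 0 hours, the next injection is the one due that morning, and the bullets do not mention it. The general schedule then leaves it due, and the holiday falls a day late.

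This sits badly with the rule's own conditions. The lower 1 mg dose may restart only once SBP is at least 85 mmHg, yet 3 mg stays due in someone just confirmed below 85 mmHg. For a symptomatic participant at 85 to 89 mmHg, only the symptom condition is unmet.

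At stake are participant safety and uniform handling of the same event across sites.

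**Working it through.** **1. Tracing the rule.** Day D is the day of the trigger, in an active participant still on 3 mg, with the restart conditions met.

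| Confirmed trigger | Day D | Day D+1 | Day D+2 |
|---|---|---|---|
| 4 hours post-dose | 3 mg already given | skip | 1 mg |
| 0 hours, literal text | 3 mg still due | skip | 1 mg |
| 0 hours, with the fix below | skip | 1 mg | 1 mg |

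The 0-hour reading on Days 3 and later is taken as pre-dose, as Table 2-2 labels it on Days 1 and 2.

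Day 2 has one extra feature. With morning doses at about the same time, the Day 1 24-hour reading and the Day 2 0-hour reading coincide. This is an inference; Table 2-2 does not say it. Treated as Day 1, a confirmed trigger gives skip on Day 2 and 1 mg on Day 3. Treated as Day 2, it gives 3 mg on Day 2, skip on Day 3 and 1 mg on Day 4.

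Three cases fall outside the gap. SBP below 100 mmHg at randomization is excluded (Section 6.2), which rules out a Day 1 pre-dose trigger under the two threshold bullets. From Day 7 a confirmed threshold trigger means discontinuation, and so does one after dose reduction (Section 7.4.2).

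**2. Exposure if the dose were given.** Table 5.5-1 gives geometric mean AUC for 3 mg daily in healthy participants: 3,420 ng·h/mL on Day 1 and 9,070 on Day 14. Assume mono-exponential accumulation.

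- Accumulation R = 9,070 / 3,420 = 2.652.
- Daily carry-over r = 1 − 1/R = 0.623.
- Day D exposure in Day 1 units, dose given: 1 + r + … + r^(D−1). Dose withheld: the same sum minus 1.

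| Day of trigger | Given | Withheld | Ratio |
|---|---|---|---|
| 2 (reading treated as Day 2) | 1.62 | 0.62 | 2.6 |
| 3 | 2.01 | 1.01 | 2.0 |
| 4 | 2.25 | 1.25 | 1.8 |
| 5 | 2.40 | 1.40 | 1.7 |
| 6 | 2.50 | 1.50 | 1.7 |

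In AUC terms, Day 3 is 6,878 versus 3,458 ng·h/mL and Day 6 is 8,540 versus 5,120. Section 5.5 also reports: "With multiple doses of 1 mg and 3 mg QD for 14 days, up to 2.5-fold (1 mg) and 2.7-fold (3 mg) accumulation". With R = 2.5 the Day 3 and Day 6 ratios are 2.04 and 1.72; with R = 2.7 they are 1.97 and 1.65.

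The fix gives 1 mg on a day the current text skips, so the later days need checking too. Taking 1 mg as 1/3 unit (dose proportionality, Section 5.5), a Day 3 trigger gives, for Days 3/4/5:

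- literal text: 2.01 / 1.25 / 1.11, total 4.38;
- fix: 1.01 / 0.96 / 0.93, total 2.91.

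For any trigger day the fix is lower by 1 on Day D, by r − 1/3 = 0.29 on Day D+1 and by r² − r/3 = 0.18 on Day D+2.

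**3. How often.** The plan gives no rate of pre-dose triggers. For a participant in hospital through Day 6, scheduled readings after the first dose number 7 (Day 1) + 4 (Day 2, counting its 0-hour reading as the Day 1 24-hour one) + 4 × 4 (Days 3 to 6) = 27. Five of these are pre-dose: one each morning of Days 2 to 6. Assume triggers are spread evenly over readings, and that 5% to 15% of the 36 active participants have a first trigger on Days 1 to 6 (the placebo range in Section 10.1, borrowed). Then:

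- 36 × 0.05 × 5/27 = 0.33
- 36 × 0.15 × 5/27 = 1.00

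The count scales in proportion to the assumed rate.

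**The case against.** The strongest reply is that Section 7.4.1 never orders the morning dose to be given, and that other text makes it unlikely. Section 7.4 rests decisions to reduce or stop on the investigator's assessment. Section 5.1 requires that a physician be contacted and the medical monitor notified. Section 8.1 requires stopping for an adverse event when continuing is judged not to be in the participant's interest. Section 9 requires immediate safety concerns to be discussed with the sponsor. The stated holiday also points away from dosing straight after a confirmed trigger.

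Most of this stands. A reader might infer that participants would in practice receive 3 mg while hypotensive; the documents do not support that. But none of these provisions directs a same-day hold that keeps the participant on the holiday-then-1 mg path. The decision named in Section 5.1 is "as to whether an ambulatory unscheduled study visit or hospitalization is required based on overall clinical assessment", and Section 9 speaks of continuing or discontinuing treatment. The safeguards reduce the risk without supplying the missing instruction.

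A reader might also infer that the plan contradicts itself on Day 2. That is too strong: the outcome turns on how one morning reading is labelled. If calendar days are used, only the Day 2 instruction remains, which is the same gap as on Days 3 to 6.

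Nor does investigator judgement set the third bullet apart. Section 7.4 puts all three bullets under that judgement, and all three share the next-day skip.

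**Conclusion.** The gap is real and of low severity. For a trigger confirmed at 0 hours on Days 2 to 6 in a participant still on the initial dose, the literal rule leaves that morning's dose due and skips the following one, whereas a post-dose trigger is followed by no further 3 mg. Day 2 adds a labelling ambiguity.

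The exposure ratios show the size of the difference if the dose were given. They come from healthy-participant AUCs and a simple accumulation model. They describe exposure, not harm, and every as-written value stays below the intended steady state of 2.65 Day 1 units. The frequency of about 0.3 to 1.0 active participant rests on the even-spread assumption and the borrowed placebo rate; it shows only that the case is uncommon but foreseeable.

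A reader might infer an effect on the primary result. There is none from this gap: a confirmed trigger under the two threshold bullets already counts as a hypotension event before the dosing decision arises.

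**What to change.** Add to Section 7.4.1, for all three bullets:

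> If the qualifying reading is obtained before that day's injection, the injection waits for the 30-minute repeat, where a repeat is required. If the trigger is confirmed (or, for the third bullet, judged by the investigator to preclude dosing at the initial level), that day's dose is the one skipped. Dosing resumes at 1 mg the following day if SBP is at least 85 mmHg and, where applicable, symptoms have resolved.

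This keeps the one-day holiday: 48 hours between doses, the same as after a post-dose trigger. It also gives Day 2 a single outcome (skip Day 2, 1 mg on Day 3) under either label. Skipping the next day as well would lower exposure further (1.01 / 0.63 / 0.73 for a Day 3 trigger) but would turn the stated one-day holiday into two days.

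The cost is a few lines in an amendment, with no added visits, staff or participants. Table 9.5-1 footnote b already covers a delayed dose. The downside is that a Day 5 pre-dose trigger loses its dosed Day 5 PK profile, which feeds the secondary endpoint. In partial return, a Day 4 pre-dose trigger can keep a 1 mg Day 5 profile; the current text skips that dose.
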